1.0 Objectives

1.1 Study Objectives

The literature supports the case for an open trial of suvorexant, an orexin 1 / 2 receptor antagonist, in patients in residential treatment for substance dependence disorders, who complain of sleep disturbance. The patients will be at least 5 days post-withdrawal, in order to minimize the residual sleep complaints associated with that phase of treatment. In previous, well-designed, placebo-controlled clinical trials in patients with insomnia (1), suvorexant has been shown to be efficacious compared with placebo. However, substance dependent patients with insomnia were not included in these studies. Although, as a new sleep medication, suvorexant has been placed in Schedule IV by the FDA, the drug has not been studied in the context of its potential abuse liability when administered at bedtime at the therapeutic dose among patients in residential treatment for substance dependence disorders. We will therefore incorporate a modified abuse liability protocol in this pilot study.

Importantly:

1. Data from animal models of opioid dependence suggest that orexins may be involved in reward seeking behavior, and that an orexin 1 receptor antagonist reduced heroin self-administration and cue-induced heroin seeking behavior in the rat (2).

2. Chronic stress and compulsive drug seeking are influenced by orexin transmission throughout the hypothalamic, extended amygdala, brainstem, and meso limbic pathways (3). These dysregulated states of hyperarousal may be normalized by an orexin 1 receptor antagonist

3. Finally, whereas the drug has been placed in Schedule IV by the DEA and the FDA, the FDA Briefing Document stated that "the potential abuse liability of suvorexant in patients with insomnia is considered to be low . . . suvorexant was not self-administered in non—human primates . . . Based on the outcome of these studies, there was no evidence that suvorexant has the potential for abuse or dependence" (1).

Hypotheses:

1. Relative to a baseline, patients being treated with suvorexant will experience an increase in total sleep time, fewer awakenings after sleep onset, and improved subjective sleep quality.

2. Relative to baseline, patients being treated with suvorexant are more likely to experience decreased total daily salivary cortisol over the course of 7 days of treatment.

3. Relative to baseline, patients being treated with suvorexant are more likely to report improved moods, and decreased ambient craving.

4. Patients being treated with suvorexant are not likely to endorse scale items associated with abuse liability 30 minutes after drug administration or the following morning.

1.2 Primary Study Endpoints

- 1) To determine if patients taking suvorexant will have improved sleep quality (increased total sleep time, fewer awakenings), as measured through, sleep wrist actigraphy, actigraphy logs, modified Pittsburgh Sleep Quality Index (PSQI), and modified Insomnia Severity Index (ISI).
- 2) To assess whether or not patients endorse scale items on a modified abuse liability assessment battery.
- 3) To determine if associations between daily reports of mood, stress, craving and sleep using Ecological Momentary Assessment (EMA data) change during the course of the study.
- 4) To determine if patients taking suvorexant will have a decrease in total daily salivary cortisol over the course of the study by collecting samples at five time points for two consecutive days at two different times in the study.

1.3 Secondary Study Endpoints

1) To assess reactivity of EMA ratings of craving and mood in response to naturally occurring stressors, determining if these associations change during the course of medication.

2) To use advanced statistical techniques to holistically characterize systemic dysregulation (including self-reported daily mood, stress and craving) and emerging patterns of re-regulation while taking suvorexant.

2.0 Background

2.1 Scientific Background and Gaps

It is now generally recognized that a number of factors contribute to the heightened risk of relapse in patients with substance use disorders (SUDs). These elements include, but are not limited to: 1) dysregulation of the HPA axis; 2) sleep complaints (including delayed sleep onset, time awake after sleep onset, total sleep time, and/or complaints of poor sleep quality); and 3) negative moods, ambient and cue-related craving and anhedonia (4-7). Persistent sleep disturbances following withdrawal from drugs of abuse are common and frequently continue over the course of a typical 28 to 30 days stay in residential treatment. Sleep abnormalities (8) have been associated with HPA axis dysregulation. Together, these findings suggest that complaints of insomnia in patients with alcohol or opioid dependence may represent an important but relatively untreated element in the complex neuropsychobiology contributing to risk of relapse.

2.2 Previous Data

The general study design of this research proposal builds on a NIDA funded study (Prescription Opioid Dependence: Physiology, Emotion & Treatment Outcome (R01 DA035240; STUDY 00044050)) that robustly predicted treatment outcomes in a cohort of patients with opioid dependence. Sleep complaints, and changes in daily and within day craving and mood and salivary cortisol over time, were assessed in a cohort of opioid dependent patients. In a subsample (n=13) of patients who remained in residential treatment for a period of 60 days; 5 relapsed while 8 remained abstinent 90 days after residential treatment discharge. These subjects were assessed for cortisol and sleep at two time points approximately 30 and 60 days following detox. Cortisol levels were assessed 5 times per day for two successive days during each data assessment period. There was no difference between those that relapsed or abstained during the initial assessment. However, cortisol levels were decreased in those that abstained and remained constant in those that relapsed after 60 days of treatment (P=0.007). Sleep was also objectively assessed with actigraphy across the full 12 day data collection period. Again, there was no difference between those that relapsed and those that did not during the first assessment period, but those that abstained demonstrated an increase in total sleep time while total sleep time in those that relapsed remained constant (P=0.048). In summary, an improvement in both cortisol and sleep during the 60 days of residential treatment was associated with abstinence of at least 90 days post discharge.

2.3 Study Rationale

Sleep complaints during the first weeks following detoxification should be considered a result of drug withdrawal, meeting the DSM-V criteria of substance induced sleep disorder- insomnia type (9). We can anticipate that HPA axis activation occurs in all phases of insomnia symptoms, i.e., substance induced sleep disorder – insomnia type, acute insomnia or chronic insomnia. Sleep complaints were common among opioid dependent patients in residential treatment for 30 days following medically assisted withdrawal in our NIDA-supported study (R01 DA035240; STUDY 00044050)). Patients who remained in residence for 60 days or more, showed either a worsening or an improvement in sleep symptoms. Individuals whose total sleep time increased over the 60-day period were more likely to remain abstinent following discharge than patients whose total sleep time decreased. At this juncture, there has been no systematic study on the effects of suvorexant on sleep complaints at any stage of recovery from opioid or alcohol dependence.

Neuroadaptations that occur in the course of addiction disrupt the normal function of the HPA axis. The HPA axis is a major neuroendocrine system that controls reactions to stress and regulates many body processes, including sleep, mood, and emotions. When patients are withdrawn from drugs of abuse, they experience a cluster of symptoms, including diminished motivation for natural rewards (anhedonia), an increase in reward thresholds, hypersensitivity to stress, chronic irritability, emotional pain, dysphoria, and significant sleep disturbances. These symptoms have been described in the early stages of withdrawal from alcohol, opiates, cocaine, cannabis, stimulants, and polysubstance abuse, and are thought to significantly contribute to patient relapse. In numerous patients, these symptoms are present for several months following withdrawal, and many patients continue to complain of sleep disturbances even when utilizing currently available prescription and nonprescription sleep medications.

A medication that can improve sleep and normalize HPA axis function may help to alter mood and craving in patients with alcohol and/or opioid drug dependence. Suvorexant, an orexin 1/2 receptor antagonist, is a new type of sleep medication that works not only on the sleep response, but also on mood and emotion (1). Whereas orexin 2 receptors influence sleep, a compound that blocked orexin 1 receptors reduced heroin self-administration and cue-induced heroin seeking behavior in rats (2). Brain areas that are influenced by orexin transmission are involved in the regulation of responses to chronic stress and compulsive drug seeking (3). In summary, suvorexant may be a more efficacious medication for SUD patients with sleep disturbance, as it works on brain systems associated with mood and emotions, as well as sleep.

3.0 Inclusion and Exclusion Criteria

3.1 Inclusion Criteria

- 1. Sex: male or female
- 2. Age: 21-64 (inclusive) years old
- 3. Caron Foundation residential alcohol or opioid dependent patients that have a history of daily or near daily substance use for the month prior to admittance. Group 1: At least 5 days post medically assisted withdrawal for alcohol dependence, and complain of problems falling asleep, remaining asleep after sleep onset, or poor sleep quality on current sleep medication (antidepressant/melatonin) for at least 3 days. Group 2: At least 5 days post medically assisted withdrawal for opioid dependence and complain of problems falling asleep, remaining asleep after sleep onset, or poor sleep quality on current sleep medication (antidepressant/melatonin) for at least 3 days.
- 4. Fluent in written and spoken English.

3.2 Exclusion Criteria

- 1. Patients who are concurrently receiving a psychoactive drug for the treatment of an Axis I disorder, but not including sedating antidepressants trazadone or mirtazapine that have been prescribed for the treatment of sleep disturbance.
- 2. Patients with current major depressive disorder greater than mild or moderate, schizophrenia, bipolar disorder, or a history of traumatic brain injury.
- 3. Patients with a history of narcolepsy or REM related phenomenon.
- 4. Patients with chronic respiratory problems including asthma, COPD, or other respiratory issues that can lead to sleep disturbances at night.
- 5. Patients with current suicidal ideation or a history of previous suicide attempts.
- 6. Patients with severe liver impairment.
- 7. Women who are pregnant or breastfeeding.
- 8. Patients who are severely obese.
- 9. Decisional impairment
- 10. Prisoners or under legal mandate.
- 11. On any medication that would interfere with study participation

Page 5 of 27 (v.04/27/2020)

- 12. Hypersensitivity to medications in the same class as suvorexant
- 13. Any chronic conditions or exclusionary criteria that would prevent participation in the study or lead to participant at risk of untoward effect because of participation in the study.

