4.2 Recruitment process

Recruitment will use a two-step process:

- The Caron based study coordinator will complete a comprehensive REDCap screening and eligibility checklist to verify study eligibility based on established inclusion/exclusion criteria. It will be reviewed with the study coordinator at Hershey Medical Center (HMC) and the PI or his designee. If a Subject is deemed eligible to participate in the research based upon the preliminary assessment and if aggregable by the HMC coordinator and the PI of his designee, the Caron-based study coordinator will approach the participant to inquire about possible interest in the study. This study coordinator will review the study design, suvorexant information packet, and the inclusion/exclusion criteria with each prospective research participant.
- $\circ~$. Only subjects approved by the Hershey staff (study coordinator at Hershey Medical center and the PI or his designee) will be asked to review and sign an informed consent form if they wish to participate.

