7.4.6.5 Prior and Concomitant Therapy

The subjects recruited will be current patients in a residential facility for the treatment of alcohol or opioid dependence. Since the doctors at Caron will be approving patient eligibility, they will know current and past patient medication regimes. Subjects may be taking concomitant medicines/therapies for various reasons at the treatment center. The pharmacy staff at Caron will also know which medications may not be permitted to take with the medication during the study, due to potential counteracting affects. Patients who are concurrently receiving a psychoactive drug for the treatment of an Axis I disorder excluding sedating antidepressants that have been prescribed for the treatment of sleep disturbance, will be excluded, as described in section 3.2.

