11.0 Risks

Medication: Suvorexant is a new class of approved hypnotic drug that acts as an orexin 1 /2 receptor antagonist, suppressing wakefulness. It has been approved for the treatment of insomnia in adults at a dose of 10 or 20 mg – for complaints related to sleep onset and/or sleep maintenance. Adverse reactions which were reported to the FDA included central nervous system depression, amnesia, hallucinations, complex sleep – related behavior,

exacerbation of symptoms of depression, suicidal ideation and potential substance abuse, and impaired next day mental alertness. Common, but less serious, reactions included somnolence, headache, dizziness, abnormal dreams, diarrhea, cough, sleep paralysis, and cataplexy like symptoms (1).

Suvorexant should not be used concurrently with alcohol or a CNS depressant. Suvorexant should not be given to patients to patients who have a hypersensitivity to drugs of the same class. Suvorexant should not be given to patients with narcolepsy, to patients with major depression or impaired respiratory function. The drug should be used with caution in patients with a history of alcohol or drug abuse; but, complaints about insomnia are highly prevalent in this group of patients – and insomnia is strongly associated with risk of relapse following a period of abstinence. While the patients in the proposed study will have a history of current alcohol or drug dependence, they are all in residence in a treatment facility where they will be closely monitored. We will be employing a modified abuse liability protocol to assess the relative risk of developing some form of dependence on suvorexant. Importantly, neither tolerance nor withdrawal effects were observed with suvorexant in the premarketing studies. Suvorexant was not self-administered in non-human primate models.

As per the exclusion criteria, we will not be including pregnant or nursing female patients or patients with a current or history of major psychiatric disorder including depression, schizophrenia, or bipolar disorder; and, we will be excluding patients with current suicidal ideation and/or a past history of suicidal behavior.

Actigraphy: There is no known risk to wearing the wrist actigraphs. A minor skin rash may develop from the wristband, but this risk is very slight.

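### Section 11 says patients with current or past depression are excluded, but Section 3.2 item 2 excludes only current MDD above a severity threshold, so the trial can dose patients its own risk section says are kept out

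*Combined protocol and SAP*

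**What the plan says.** Section 3.2, item 2, lists as an exclusion: "Patients with current major depressive disorder greater than mild or moderate, schizophrenia, bipolar disorder, or a history of traumatic brain injury". For depression this item sets two conditions: the disorder must be current, and it must exceed a stated severity.

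Section 11.0 (Risks, medication paragraphs) returns to eligibility in a sentence that opens "As per the exclusion criteria, we will not be including pregnant or nursing female patients or patients" and goes on to name "patients with a current or history of major psychiatric disorder including depression, schizophrenia, or bipolar disorder". For depression it sets neither condition: no severity is given, and history counts as well as current illness.

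Earlier in Section 11.0, among the drug precautions, the protocol says "Suvorexant should not be given to patients with narcolepsy, to patients with major depression or impaired respiratory function", again without a severity qualifier. The adverse reactions listed there include "exacerbation of symptoms of depression, suicidal ideation and potential substance abuse".

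**The concern.** Section 11 claims to report the exclusion criteria and reports them wrongly on depression. Anyone who judges the risk of the trial from that section would conclude that nobody with current or past depression receives suvorexant. A coordinator who follows Section 3.2 correctly may enrol such a patient.

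The difference matters because it concerns safety. The protocol itself names worsening depression and suicidal ideation among the reactions reported for the drug, so the Section 11 statement reads as an assurance that the criteria do not deliver.

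**Working it through.** No arithmetic applies; the check is a comparison of text. Both passages are current protocol text, and neither is redacted or part of an amendment log.

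**Step 1: which rule governs screening.** Sections 4.1 and 4.2 have the coordinator check patients against the inclusion and exclusion criteria, and Section 7.4.6.5 refers to Section 3.2 by number. No section tells anyone to screen from Section 11. Section 3.2 is the operative rule.

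**Step 2: the two statements side by side.**

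| Patient | Section 3.2 item 2 | Section 11.0 |
|---|---|---|
| Severe current MDD | excluded | excluded |
| Moderate current MDD | not excluded on the plain reading | excluded |
| Mild current MDD | not excluded | excluded |
| Past MDD, now remitted | not excluded | excluded |

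Reading the word depression in Section 11 narrowly, as MDD only, leaves the table unchanged. Reading item 2 more strictly, so that moderate MDD is also out, changes the second row but leaves mild and past MDD in conflict.

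**Step 3: whether the mismatch is confined to depression wording.** The same Section 11 sentence matches Section 3.2 on pregnancy and breastfeeding (item 7) and, in substance, on suicidality (item 5). It is therefore a summary of the list that departs from it on depression.

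**Step 4: whether another provision closes the gap.**

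- Item 1 removes patients taking a psychoactive drug for an Axis I disorder. Untreated mild or moderate MDD and remitted MDD pass, and trazodone or mirtazapine prescribed for sleep is allowed.
- Item 5 removes suicidal ideation and past attempts, not depression as such.
- Item 13 removes patients with conditions that would "lead to participant at risk of untoward effect because of participation in the study". This is a matter of judgement and states no depression rule.
- Section 4.2 adds a study-team approval ("Only subjects approved by the Hershey staff"), and Section 7.4.6.5 adds physicians ("Since the doctors at Caron will be approving patient eligibility, they will know current and past patient medication regimes"). Neither states a depression rule; the latter section repeats only the psychoactive-drug exclusion.
- Section 7.2.1 schedules the MINI and the HAM-D on Day 0. They supply the information needed to apply a rule, but the HAM-D is described as a continuous measure and no eligibility cut-off is given.

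These provisions narrow the gap. None of them makes the two sections agree.

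**The case against.** The best case for leaving the text alone is that Section 11 is a narrative summary that defers to Section 3.2, so the operative rule is known and only a loose sentence is at fault. The first half of that stands. A reader might infer that nobody can tell which section governs, or that staff will screen the same patient differently. The documents do not support that, because Sections 4.1, 4.2 and 7.4.6.5 all point to the criteria. But if Section 3.2 governs, Section 11 misdescribes who will be dosed, and that still needs correcting.

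A reader might also infer that depression is assessed too late or too thinly to apply any rule. That is not supported either. Table 1 lists the MINI Screen/MINI 7.0.2 and the HAM-D on Day 0, Section 7.2.1 says this assessment further evaluates eligibility, and the first suvorexant dose is on Night 2.

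A third stronger reading is that the precaution "Suvorexant should not be given to patients with narcolepsy, to patients with major depression or impaired respiratory function" is itself a trial eligibility rule that Section 3.2 breaches. It stands among general drug warnings, one of which urges caution in people with a history of alcohol or drug abuse, the population under study. It supports the point but does not carry it. The conflict rests on the sentence that claims to restate the criteria.

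Finally, the safeguards are real: items 1, 5 and 13, clinician approval, residential care, seven nurse-administered doses and nightly questioning about adverse events (Section 19.2). They reduce the risk without making Section 11 true.

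**Conclusion.** The point holds, and the text is wrong as written: a patient with mild current MDD, moderate current MDD on the plain reading, or past MDD can be enrolled in compliance with item 2 although Section 11 says such patients are excluded. It should be fixed, because the statement concerns safety and the correction is cheap.

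Its size is limited. The documents give no prevalence of depression at the site, so no number of the 36 planned participants can be put on it. No endpoint, contrast or sample size is affected, and nothing here shows that the trial is unsafe or its results biased.

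The conclusion assumes that item 2 is read in its ordinary sense, with only disease above moderate excluded. Under a stricter reading the conflict shrinks to mild and past MDD but does not disappear.

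**What to change.** Make Section 3.2 item 2 and Section 11.0 state the same rule. The choice is clinical, and either of two routes works.

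1. **Exclude any current MDD.** Amend item 2 accordingly, which is what the Section 11 precaution implies, and state whether past MDD is excluded. If it is not, delete the reference to a history of depression from Section 11. The Day 0 MINI Screen/MINI and HAM-D are already scheduled before the first dose and can be used to apply the rule. The cost is the edit and somewhat slower recruitment.
2. **Keep a severity threshold.** If it is intended, reword item 2 to exclude severe current MDD, which removes the doubt over moderate disease. Correct Section 11 to say that patients with mild or moderate current MDD, or past MDD, may be dosed, and give the safety rationale in the light of that section's own warning. The cost is the wording and the written rationale.

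Neither route requires a new assessment or a change to the analysis.

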3.3 Early Withdrawal of Subjects

3.3.1 Criteria for removal from study

Subjects are free to withdraw at any time without any influence impacting their ongoing treatment. If a patient experiences side effects, these will be documented and reported to the FDA, as required.

